## 2.2 STUDY RATIONAL & KNOWN POTENTIAL BENEFITS

The recognition that terminal duct obstruction from hyperkeratinization of the ductal epithelium on meibomian glands is a core mechanism behind meibomian gland dysfunction (MGD) is consistent with clinical experience demonstrating that effective treatments for MGD require resolution of ductal obstruction and evacuation of glandular contents (Nichols et al, 2011; Lane et al, 2012; Blackie et al, 2015). Warm compresses and thermal/mechanical devices (e.g., LipiFlow) are used in an attempt to raise the internal temperature of the meibomian glands over the normal melting point for meibum (i.e., 32°C to 40°C) resolving the terminal duct obstruction (Lane et al, 2012). Unfortunately, warm compresses are unable to achieve this benefit for severely obstructed glands which can have a melting point > 40°C.

Finis and colleagues (2014), conducted a prospective, randomized, observer-masked trial in 40 patients with MGD: 19 patients were randomized to LipiFlow and 16 patients were randomized to standard of care (i.e., twice-daily lid warming, massage, and cleaning of the lid margin) for 3 months. LipiFlow and standard of care demonstrated significant improvements from baseline in symptoms, measured by SPEED, and in the number of expressible glands by 1 month. Consistently observed benefits for devices designed to treat glandular obstruction include:

- 1) Improvement in the meibum gland score (MGS) (0 to 45 scale);
- 2) Increases in the number of meibomian glands yielding liquid secretion (MGYLS) (0 to 15 scale);

3) Increased Tear Break-up Time (TBUT); and

- 4) Improved Total OSDI, SPEED and eye dryness scores (measured using a visual analogue scale [VAS]) (Blackie et al, 2015).

While there are no approved pharmacological treatments for terminal duct obstruction from hyperkeratinization associated with MGD, compounds that reduce disulfide bonds (S-S) have shown promise. Akyol-Salman and colleagues (2010) used N-acetyl-cysteine (NAC) in 20 patients with MGD and demonstrated a statistically significant improvement in TBUT and symptoms (e.g., itching) by 1 month (Akyol-Salman et al, 2010; Akyol-Salman et al, 2012). Selenium sulfide as a 0.5% ointment has also been applied to the lid margin as a treatment for seborrheic blepharitis (Bahn, 1954).

Eleven patients were randomized to Cohort 1, Group 1 (0.1%, twice-weekly) between September 10th, 2018 and October 19th, 2018 in ongoing clinical study AZ201801. Twelve patients were randomized to Cohort 1, Group 2 (0.5%, twice-weekly) between October 19th, 2018 and February 20th, 2019. Ten patients were randomized to Cohort 1, Group 3 (1.0%, twice-weekly) between April 22nd, 2019 and June 19th, 2019.

As specified in Protocol Amendment # 2 dated January 2019, the primary efficacy variables for MGD included change from baseline to month 3 in Meibomian Gland Score (MGS) and measures of Total Ocular Surface Disease Index (OSDI). Least Square (LS) mean changes from baseline (larger scores signal improvement) for MGS at month 3 were  $4.5 \pm 2.0$  ( $p = 0.025$ ) for the Vehicle Group;  $1.2 \pm 2.0$  ( $p = 0.56$ ) for the AZR-MD-001 0.1% Group (sub-therapeutic dose);  $4.9 \pm 2.1$  ( $p = 0.02$ ) for the AZR-MD-001 0.5% Group; and  $12.2 \pm 2.4$  ( $p < 0.0001$ ) for the AZR-MD-001 1.0% Group. Total OSDI showed the same pattern of results. Least square (LS) mean changes from baseline (smaller scores signal improvement) for Total OSDI at month 3 were  $0.0 \pm 3.4$  ( $p = 0.99$ ) for the Vehicle Group;  $9.5 \pm 3.8$  ( $p = 0.01$ ) for the AZR-MD-001 0.1% Group;  $-6.9 \pm 4.0$  ( $p = 0.08$ ) for the AZR-MD-001 0.5% Group; and  $-12 \pm 5.1$  ( $p < 0.01$ ) for the AZR-MD-001 1.0% Group. The difference of 12 between the Vehicle and AZR-MD-001 1.0% Groups was statistically significant ( $p = 0.03$ ) and the results appear dose responsive.

Based upon positive efficacy and safety results from clinical study MGSS1 for the ocular application of selenium disulfide shampoo (2.5%) and from Clinical Protocol AZ201801 for AZR-MD-001 (0.5% and 1.0%), Azura Ophthalmics is further evaluating the safety, tolerability and effectiveness of AZR-MD-001 (0.5%) ointment/semi-solid drug, surfactant free, in patients with MGD.

## 2.3 RISK/BENEFIT ASSESSMENT

### 2.3.1 KNOWN POTENTIAL RISKS

Selenium sulfide is used as an anti-fungal and anti-dandruff ingredient in commercially available shampoo (i.e., Selsun Blue, Exsel, Selsun, and Seleen). Selenium sulfide is not absorbed through the skin following topical use and is considered safe for topical use. In 15 people who applied 2.5% selenium sulfide to the torso overnight no appreciable levels of selenium sulfide were measured in the serum or in the urine (Kalivas, 1993). Additionally, in a 1-year exposure study, 16 people who washed their hair weekly with 1% shampoo monthly did not demonstrate urine selenium levels that were different from 8 control subjects (Cummins and Kimura, 1971). These data support the conclusion that selenium is not absorbed through intact skin. Systemic absorption of selenium has been reported with open lesions on the scalp (Sternberg et al, 1964). Based upon these findings, systemic exposure to selenium disulfide following topical, ocular dosing of AZR- MD-001 ointment/semi-solid drug is considered a minimal risk.

Selenium can have inhibitory effects on proteins and enzymes by reacting with thiol or sulfhydryl groups in proteins. Specifically, selenium sulfide, in vitro, was shown to inactivate the free sulfhydryl groups on human epidermis and mouse liver (Flesch, 1953).

Ocular toxicity studies with selenium sulfide have been completed in rabbits. Selenium sulfide was administered to the conjunctival sac of rabbits to compare the toxicity of 0.5% selenium disulfide ophthalmic ointment to that of 2.5% selenium sulfide shampoo (Rosenthal and Adler, 1962). Administration of the 0.5% selenium disulfide ophthalmic ointment was not associated with any ocular toxicity while 2.5% selenium sulfide shampoo was associated with chemosis, redness, corneal clouding, edema, and “total staining” in all eyes within 2 hours of administration. It is unclear if 2.5% selenium sulfide or if another ingredient of the shampoo is bothersome to the ocular surface.

To further evaluate the ocular tolerability and ocular toxicity of selenium disulfide, Azura Ophthalmics evaluated AZR-MD-001 ointment/semi-solid drug in a preclinical study at three concentrations (i.e., 0.5%, 1.0%, and 2.5%) over three dosing frequencies (i.e., twice weekly once daily and twice daily) with a standard clinical dosing volume (i.e 5  $\mu$ L) and with an exaggerated dosing volume (i.e., 25  $\mu$ L) for the highest concentration of 2.5%. Thirty-nine female albino rabbits (New Zealand White strain) were included across 10 groups (see Table 2–1). All groups were treated for 7 days. During the study, eyes were evaluated macroscopically (Draize’s scale) and under the slit-

lamp (McDonald-Shadduck’s scale). At the end of the study, eye globes were histopathologically examined.

Table 2–1 Dose Groups Included in the Pre-Clinical Evaluation of AZR-MD-001 Ointment/semi-solid Drug

Group n°	Treatment (concentration)	Dose Regimen (Right eye)	Number of animals		
			Series 1	Series 2	Series 3
4	AZR149 (0.5% - 5 µL)	Twice weekly (q3.5d ± 1d) ocular topical application from Day 1 to Day 7 onto the lower lid margin	--	3	--
3	AZR150 (1% - 5 µL)		--	3	--
1	AZR141 (2.5% - 25 µL)		3	--	--
2	AZR140 (Placebo - 25 µL)		3	--	--
8	AZR149 (0.5% - 5 µL)	Once daily ocular topical application from Day 1 to Day 7 onto the lower lid margin	--	6	--
7	AZR150 (1% - 5 µL)		--	3	--
5	AZR141 (2.5% - 25 µL)		6	--	--
6	AZR140 (Placebo - 25 µL)		6	--	--
9	AZR149 (0.5% - 5 µL)	Twice daily (7h ± 1h) ocular topical application from Day 1 to Day 7 onto the lower lid margin	--	6	--
10	AZR141 (2.5% - 5 µL)	Once daily ocular topical application from Day 1 to Day 7 onto the lower lid margin	--	--	3*

\*Note 1: These 3 animals were already treated once daily with AZR149 0.5% during 7 days before joining the series 3 (without wash-out period).

### 2.3.2 ASSESSMENT OF POTENTIAL RISKS AND BENEFITS

The predominate conventional treatments for obstructive MGD entail eyelid hygiene (e.g., lid washing and use of preservative-free artificial tears), applying warm compresses to the eyelid, and gentle lid massaging (Olson et al, 2003; Romero et al, 2004; Yoo et al, 2005; Perry et al, 2006; Pinna et al, 2007; Souchier et al, 2008; and Foster et al, 2009). Eyelid-warming devices have also been employed in the treatment of patients with MGD (Goto et al, 2002; Mitra et al, 2005; Matsumoto et al, 2006; Geerling et al, 2011; Lane et al, 2012). Unfortunately, these treatments are relatively invasive, time consuming and uncomfortable for patients. There are currently no approved pharmacologic treatments for MGD. Thus, there is a medical need for a less invasive, pharmacologic treatment for MGD and associated evaporative DED.

Given the high unmet medical need, the reversibility of ocular findings with selenium disulfide shampoo (2.5%) in clinical study MGSS1, and the observed safety and efficacy for both MGD and evaporative DED in clinical protocol AZ201801, the risk/benefit profile of AZR-MD-001 ointment/semi-solid drug supports continued development in the proposed study design.

### 3 OBJECTIVES AND ENDPOINTS

Table 3–1 Table of Objectives, Endpoint, and Endpoint Justification

OBJECTIVES	ENDPOINTS	JUSTIFICATION FOR ENDPOINTS
Cohort 1 and Expansion Cohort		

To evaluate the safety, tolerability and pharmacodynamics of AZR-MD-001 ointment/semi-solid drug applied to the lower lid twice-weekly for up to 3 months compared to its vehicle in patients with meibomian gland dysfunction (MGD).
	
Safety/Adverse Events:
 
 
● Incidence rates of each treatment-emergent adverse event summarized by primary system organ class and preferred term.
 
● Tables for all treatment-emergent adverse events regardless of causality.
 
● Tables for all treatment-emergent adverse events considered to be treatment-related.
 
● Shift tables for safety variables (e.g., IOP, biomicroscopy, and ophthalmoscopy).
 
 
Signal of Efficacy: Primary Efficacy for MGD:
 
 
● Change from Baseline to Month 3 in meibum gland secretion score (MGS) (0 to 45 scale)
 
● Change from Baseline to Month 3 in Total OSDI
 
	
The endpoints for safety and tolerability are all commonly used in ophthalmic drug trials.
 
Consistently observed benefits for devices designed to treat glandular obstruction and for AZR-MD-001 ointment/semi-solid drug include:
 
 
● Improvement in the meibum gland secretion score (MGS) (0 to 45 scale);
 
● Improved Total OSDI (Blackie et al, 2015).
 

## **4 STUDY DESIGN**

### **4.1 OVERALL DESIGN**

This is a multicenter, investigator-masked, vehicle-controlled, randomized, parallel group study comparing AZR-MD-001 (0.5%) ointment/semi-solid drug and AZR-MD-001 vehicle dosed twice-weekly in the evening.

Patients with MGD will be randomly assigned in a 1:1 ratio to receive either a single concentration of AZR-MD-001 ointment/semi-solid drug (i.e., 0.5%) or AZR-MD-001 vehicle.

For all dose groups a screening visit will be followed by a baseline visit 14 days later (qualification period). At the end of the qualification period patients who still exhibit signs of MGD and who can comply with dosing instructions will be enrolled into a 3-month treatment period. The study flow is shown in Figure 1.

### **4.2 PROCEDURES**

#### **4.2.1 Screening**

Participants will be identified by the sites and brought in for screening visits. Participants may be provided with the Participant information sheet in advance, though will only sign consent during the visit with the study team. Written informed consent will be obtained from each participant prior to commencing any study related activities. Written and verbal versions of the Participant Information and Informed Consent will be presented to the participants detailing: the exact nature of the trial; what it will involve for the participant; the implications and constraints of the protocol; the known side effects and any risks involved in taking part. The participant must personally sign and date the latest approved version of the Informed Consent form.

It will be clearly stated that the participant is free to withdraw from the trial at any time for any reason without prejudice to future care, without affecting their legal rights and with no obligation to give the reason for withdrawal.

The following data will be collected at the screening visit – which may be conducted over one day, or multiple days in the window before the baseline visit:

- Medical History (including ophthalmic)
- Demographics (date of birth, gender, race, ethnicity)
- Vital Signs – height, weight, pulse rate and blood pressure
- Urine pregnancy test for women of childbearing potential
- Current medications (including any washout required)
- Questionnaires completed by the participant: OSDI, SPEED, VAS
- Slit -lamp Biomicroscopy
- Tear Break up Time

- Sodium Fluorescein corneal staining
- Lissamine green conjunctival staining
- Meibomian gland evaluation
- Schirmer's test – without anesthesia
- Intraocular Pressure
- Ophthalmoscopy Examination (dilated)
- Meibography

#### 4.2.2 Baseline (Day 0)

Participants will return to the clinical site up to 14 days from screening visit. Assessments will be conducted as per the Schedule of Assessment table. If the participant is still eligible based upon results of BCVA, TBUT and meibomian gland score, the participant will be asked to “practice dose” with Vaseline in order for the study doctor to confirm their suitability and compliance with being able to self-dose. The tolerability questionnaire will be provided to participants to complete based upon this “practice dose”.

The study doctor observing the participants application of dose is required to confirm that they will be able to consistently administer the medication themselves at home by answering some specific questions about the self-dosing. If the participant is confirmed as eligible at this stage, they will be randomized into one of the 2 arms, and provided with the appropriate medication to take home, with instruction for storage and the requirement to keep and return all used and unused containers.

In order to main the blind, the person performing the Randomization and dispensing the medication must not be involved in performing any assessments with the participants.

Participants will be required to dose twice per week at bedtime. Patients will take their first at-home dose in the evening of the Baseline Visit and then 2 or 3 days of “rest” before taking the next dose (i.e., twice weekly dosing).

For example, if a patient is dosed for the first time on Monday evening, then they can dose again on Thursday or Friday. It is recommended they keep dosing on the same two days of each week. If the participant misses a dose on their “scheduled” day, they should dose the next day and then go back to the same schedule for the following weeks.

#### 4.2.3 Day 14/Month 1/Month 1.5/Month 3 (plus follow up call)

Participants will return to site at Day 14 (+/- 2 days), Month 1 (+/- 7 days), Month 1.5 (+/- 7 days) and Month 3 (+/- 2 days).

Assessments will be conducted as per the Schedule of Assessment table. Note the Ophthalmoscopy examination will be conducted undilated, unless dilation is necessary.

Participants are expected to return all used and unused containers for compliance check at each visit, with new medication dispensed.

Month 3 is the final on site study visit for participants. For any participant that withdraws early, the Month 3 assessments should be conducted at the next study visit.

The participants will be called one week (+/- 2 days) after their month 3 visit, to assess adverse events and address any issues noted since ceasing the study medication.

### 4.3. SCIENTIFIC RATIONALE FOR STUDY DESIGN

While there are no approved pharmacological treatments for terminal duct obstruction from hyperkeratinization associated with MGD, compounds that reduce disulfide bonds (S-S) have shown promise. Akyol-Salman and colleagues (2010) used N-acetyl-cysteine (NAC) in 20 patients with MGD and demonstrated a statistically significant improvement in TBUT and symptoms (e.g., itching) by 1 month (Akyol-Salman et al, 2010; Akyol-Salman et al, 2012). Selenium sulfide as a 0.5% ointment dosed up to a total daily dose of 1.0% has also been applied to the lid margin as a treatment for seborrheic blepharitis (Bahn, 1954, see the Investigator's Brochure for more detail).

Azura Ophthalmics is evaluating AZR-MD-001 ointment/semi-solid drug (selenium disulfide) as a potential treatment for MGD and associated evaporative DED. Selenium sulfide exists as a mixture of selenium monosulfide and selenium disulfide. AZR-MD-001 uses the same API as commercially available marketed products (i.e., Selsun Blue, Exsel, Selsum, and Seleen). In these shampoos selenium disulfide is used as an anti-fungal and anti-dandruff ingredient. It is marketed at a 1% concentration in non-prescription products and at a 2.5% concentration in prescription products.

Clinical Protocol AZ201801 was a multicenter, double-masked, vehicle-controlled, randomized, parallel group study carried out in 2 sequentially overlapping cohorts. Significant, dose responsive improvements for both MGS and total OSDI were observed.

Based upon positive efficacy and safety results from both clinical study MGSS1 and Clinical Protocol AZ201801, Azura Ophthalmics is further evaluating the safety, tolerability and effectiveness of AZR-MD-001 (0.5%) ointment/semi-solid drug, surfactant free, in patients with MGD.

#### **4.4 DATA REVIEW COMMITTEE (DRC)**

This study does not use a DRC.

#### **4.5 END OF STUDY DEFINITION**

A participant is considered to have completed the study if he or she has completed all phases of the study including the last visit or the last scheduled procedure shown in the Schedule of Activities (SoA), Section 1.3.

### **5 STUDY POPULATION**

The study will consist of patients with Meibomian Gland Dysfunction (MGD).

#### **5.1 INCLUSION CRITERIA**

- Male or female, 18 years of age or older at screening visit

- Capable of understanding and willing to provide written informed consent and likely to complete the entire course of study according to instructions
- Written authorization for use and release of health and research study information has been obtained
- Best-corrected visual acuity (BCVA) of 20/40 or better (Snellen equivalent), using the logarithm of the minimum angle of resolution (LogMAR) in each eye at the screening and baseline visits
- Evidence of meibomian gland obstruction (based on a meibomian gland secretion (MGS) score of  $\leq 12$  for 15 glands of the lower lid) in both eyes at the screening and baseline visits
- Reported dry eye signs and symptoms within the past 3 months
- Prior to starting screening visit procedures, patients are required to have discontinued:
  - Use of systemic antihistamines or isotretinoin for at least 1 month
  - Anti-inflammatory treatments for DED (e.g., cyclosporine ophthalmic emulsion [Restasis® or Ikervis®] or lifitegrast ophthalmic solution [Xiidra®]) for at least 3 months
  - All other prescription medications used for dry eye or MGD (e.g., antibiotics, corticosteroids, and non-steroidal anti-inflammatory drugs) for at least 2 weeks
  - LipiFlow® or other lid-heating therapy, meibomian gland probing, or therapeutic gland expression in either eye within 6 months prior to the screening visit
  - All other MGD treatments (e.g., at-home warm compress therapy, eyelid hygiene, eyelid massage, and manual lid expression) for at least 2 weeks

And

- All other topical ophthalmic preparations (including artificial tear substitutes) other than the study drops: 72 hours prior to screening visit. If artificial tear substitutes were used within 72 hours of the screening visit the visit should be rescheduled
  - Evidence of active MGD associated signs and symptoms at the screening and baseline visits:
    - Score  $\geq 6$  on the Standard Patient Evaluation of Eye Dryness questionnaire (SPEED)
    - Ocular Surface Disease Index (OSDI) questionnaire score  $\geq 13$
- And
- TBUT  $< 10$  seconds in both eyes
  - Demonstrated ability to follow dosing instructions at the baseline visit
  - A negative pregnancy test result for all women at the screening visit
  - Women of childbearing potential must have a history of bilateral tubal ligation or use oral contraceptives, implants, injectables, transdermal patch, or intrauterine device for

birth control during the study. Abstinence is not considered a reliable method of birth control. If these methods of birth control do not apply, woman of childbearing potential must have a monogamous partner who has had a vasectomy at least 3 months before the screening visit or who is of the same gender.

## 5.2 EXCLUSION CRITERIA

- Uncontrolled ocular disease (except for MGD and dry eye disease/keratoconjunctivitis sicca associated with MGD) or uncontrolled systemic disease
- Patient has glaucoma, ocular hypertension, or intraocular pressure (IOP) in either eye at screening  $\geq 24$  mm Hg as determined by Goldman applanation tonometry or has planned insertion/removal of glaucoma filtration shunts/devices during the study
- Corneal abnormality or disorder that impacts normal spreading of the tear film (keratoconus, pterygia, scarring) or corneal integrity
- BCVA worse than 20/40 in either eye at the screening or baseline visit
- Current use of punctal plugs, anticipated insertion during the study, or a history of punctal cautery in either eye at any time prior to the screening visit or anticipate such a procedure during the study
- Keratoconjunctivitis sicca secondary to destruction of conjunctival goblet cells as occurs with vitamin A deficiency or scarring, such as that with cicatricial pemphigoid, alkali burns, Stevens-Johnson syndrome, trachoma, or irradiation
- Keratoconjunctivitis sicca secondary to aqueous deficient DED
- Active ocular infection (bacterial, viral, or fungal) at the screening or baseline visits
- Corneal, conjunctival, or eyelid inflammation (including allergic, vernal, or giant papillary conjunctivitis and mucous membrane pemphigoid) that in the judgment of the investigator may interfere with the study results or the ability of subjects to complete the treatment period
- Recent (within the past 3 months of the screening visit) ocular surgery, trauma, herpes, or recurrent inflammation
- Contact lens use anticipated during the study
- Periocular application of makeup likely to impact meibomian gland function during the study or tattooing of the lids
- Use of any type of scleral lenses or sealed compartment ocular frames within 2 months of the screening visit, or planned use during the study
- Use prohibited medications (topical, topical ophthalmic, systemic and/or injectable) during the appropriate pre-study wash-out period and during the study
- Unwilling to abstain from the use of systemic medications known to cause dryness for the study duration that is not used on a stable dosing regimen for at least 30 days prior to the baseline visit
- Unwilling to abstain from the use of systemic or topical treatments for MGD or dry eye for the study duration (Including over-the-counter [OTC] artificial tears, ocular lubricants, or dietary supplements known to impact ocular surface health)
- Eyelid abnormalities that affect normal lid function in either eye other than those caused by meibomian gland dysfunction
- Diagnosis of hepatitis C infection, human immunodeficiency virus (HIV) infection, sarcoidosis, amyloidosis, active tuberculosis, or graft versus host disease
- History of anterior segment surgery or trauma that could affect corneal sensitivity (e.g., cataract surgery or any surgery involving a limbal or corneal incision) in either eye within the 12 months prior to the screening visit

- Planned anterior segment surgery (e.g., cataract surgery or any surgery involving a limbal or corneal incision) in either eye during the study period
- Meibography score at the screening visit of 4 (greater than 75% partial glands using the gestalt grading system)
- Corneal staining  $\geq 3$  (between 33 and 100 dots) using the Oxford Scheme
- Schirmer's tear test without anesthesia  $\leq 5$  mm in either eye at the baseline visit
- Known allergy or sensitivity to fluorescein, lissamine green, or the study medication or its components
- Use of medicated shampoos containing selenium (e.g., Selsun Blue, Exsel, Selsum, and Seleen) following the screening visit
- Patient is unlikely to follow study instructions or to complete all required study visits or has a condition or situation that in the investigator's opinion, may put the patient at significant risk, may confound the study results, or may interfere significantly with the patient's participation in the study
- Patient is an employee at the investigational site or is related to any member of the study staff
- Pregnant, nursing, or females of childbearing potential and not utilizing adequate birth control measures. Woman of childbearing potential may have a monogamous partner who has had a vasectomy at least 3 months before the screening visit or who is of the same gender.
- Positive urine pregnancy test at the screening visit
- Participation in another clinical trial involving a therapeutic drug or device within the past 30 days

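### Eligibility could admit patients already treated with AZR-MD-001, because the only bar is a generic 30-day rule on other trials

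*Protocol*

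**What the plan says.** The rule on earlier trials, in Protocol Section 5.2 and repeated in the synopsis, excludes "Participation in another clinical trial involving a therapeutic drug or device within the past 30 days". Neither place, nor Sections 5.1 and 5.3, has a criterion on earlier use of AZR-MD-001 or on having taken part in AZ201801.

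Two other criteria shape who could come back:

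- Section 5.2 excludes "Known allergy or sensitivity to fluorescein, lissamine green, or the study medication or its components".
- Section 5.1 requires "Evidence of meibomian gland obstruction (based on a meibomian gland secretion (MGS) score of" at most 12 in both eyes, at screening and again at baseline.

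For other treatments the protocol sets specific intervals. Section 5.1 requires patients to be free of "LipiFlow® or other lid-heating therapy, meibomian gland probing, or therapeutic gland expression in either eye within 6 months prior to the screening visit", and to be 3 months off anti-inflammatory dry eye treatment. The catch-all is "All other prescription medications used for dry eye or MGD (e.g., antibiotics, corticosteroids, and non-steroidal anti-inflammatory drugs) for at least 2 weeks", which does not name AZR-MD-001 and is shorter than 30 days in any case.

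Section 2.2 describes AZ201801, the sponsor's earlier trial of this drug in MGD, as ongoing. It reports Cohort 1 groups of 11 (0.1%), 12 (0.5%) and 10 (1.0%). Of the concentration used here it says: "Twelve patients were randomized to Cohort 1, Group 2 (0.5%, twice-weekly").

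The SAP does not use prior exposure anywhere: not in the primary models (9.1, 9.2), the sensitivity analyses (6.3, 7.3) or the subgroups (12.1).

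**The concern.** The objective is safety, tolerability and pharmacodynamics against vehicle. A person who has already used the drug brings information about both outcomes into the trial. The entry criteria then filter on that information. Those known not to tolerate the drug are removed by the sensitivity exclusion, and those with a lasting response are removed by the MGS limit. What remains is tilted towards people who tolerated the drug and either did not respond or lost their response.

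In the active arm, such patients would make tolerability look better than it would in new users. They would also pull the MGS and OSDI differences towards zero if they fail to respond again. With about 15 patients per arm, a few are enough to matter. Nothing in the SAP would reveal it, because prior exposure is neither a covariate nor the basis of any planned analysis.

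**Working it through.** **1. Who could re-enter.** Take a patient given AZR-MD-001 in AZ201801 and apply the criteria in turn.

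| Criterion | Effect on a former AZR-MD-001 patient |
|---|---|
| Other trial within 30 days (5.2) | Passes once 30 days have gone by |
| Known sensitivity to study medication (5.2) | Removes those known to be intolerant |
| MGS at most 12, both eyes, two visits (5.1) | Removes those with a lasting response |
| 2 weeks off other MGD prescriptions (5.1) | Adds nothing beyond 30 days |
| Prior AZR-MD-001 use | No criterion |

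**2. Size of the source pool.** Section 2.2 gives 11 + 12 + 10 = 33 for Cohort 1, against about 30 to be randomized here (Section 5.5). The figure is rough. Section 2.2 also reports a vehicle result without a separate count, so it is not explicit that all 33 were on active drug. Numbers for the other cohort are not in the available text.

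**3. The actual gap since dosing.** The last Cohort 1 randomization given is 19 June 2019. Assuming about 3 months of treatment, dosing ended about 19 September 2019. SAP Section 2 dates this protocol 12 March 2020, about 175 days later. The 30-day rule would therefore exclude none of these patients on account of that trial, but their gap would be well over 30 days.

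**4. The plan's own sample size, reproduced.** Inputs from Protocol Section 9.1 are MGS SDs 3.35 and 9.48 with difference 10.4, and OSDI SDs 13.01 and 6.79 with difference 15.9, at two-sided alpha 0.05. The noncentrality is difference / √((s₁² + s₂²)/n).

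- MGS, n = 12: 10.4 / √(101.09/12) = 10.4 / 2.90 = 3.58. Power is 0.914 with unequal variances (n = 11 gives 0.884).
- OSDI, n = 11: 15.9 / √(215.36/11) = 15.9 / 4.42 = 3.59. Power is 0.919 with unequal variances (n = 10 gives 0.888).

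The stated 12 and 11 per group are confirmed.

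**5. Illustrative dilution.** Suppose a share f of the active arm has zero effect. The documents give no value of f, so a range is shown. The mean difference becomes d × (1 − f). Mixing also raises the active-arm variance to s² + f(1 − f)d². For MGS at f = 0.20 the difference is 10.4 × 0.80 = 8.32, and the active variance is 89.87 + 0.16 × 108.16 = 107.18 (SD 10.35). The table gives equal-variance t-test power at 15 per arm, without and then with the added variance.

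| f | MGS | OSDI |
|---|---|---|
| 0 | 0.97 | 0.98 |
| 0.10 | 0.94 / 0.91 | 0.95 / 0.93 |
| 0.20 | 0.87 / 0.82 | 0.90 / 0.84 |
| 0.30 | 0.77 / 0.69 | 0.81 / 0.72 |

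One returner is 1/15 = 6.7% of an arm, and three are 3/15 = 20%. Under 1:1 allocation, three in the active arm corresponds on average to about six among the 30.

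**The case against.** The strongest reply is that this is only a possibility. No text says that an AZ201801 patient will enrol or that sites overlap. That is correct, and it limits the point to what eligibility permits.

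Returners would also be randomized 1:1, stratified by baseline MGS and disease duration, and the primary models adjust for baseline. So their selection balances in expectation. This stands: a systematic bias between arms is not shown. It does not answer the effect on tolerability in the active arm, or the dilution.

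There are partial safeguards. The investigator may exclude a patient for a condition or situation that "may put the patient at significant risk, may confound the study results". Medication history is taken at screening, and SAP Section 8.4 lists relevant prior medications. But the clause does not name prior exposure, so sites may apply it differently, and a listing is not an analysis.

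Four stronger readings are tempting, and the documents do not support them:

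- *Returners will be only 30 days off drug.* Thirty days is the minimum allowed. For Cohort 1 the gap at protocol issue was probably about 175 days or more.
- *All returners would be non-responders.* Some may have responded and relapsed, and could respond again. Others may have been on vehicle.
- *Returners would break the masking by recognising the active product.* Active is orange and vehicle white, but every patient handles the white practice product at baseline, so the colour risk is general. AZ201801 was double-masked, and the available text does not describe how its products looked.
- *The selenium shampoo rule needs a longer washout.* It bars "Use of medicated shampoos containing selenium (e.g., Selsun Blue, Exsel, Selsum, and Seleen) following the screening visit", which begins about 14 days before baseline. Use on the lids to treat MGD would fall under the 2-week rule for other MGD treatments, and Section 2.3.1 concludes that selenium is not absorbed through intact skin. The documents give no basis for a longer period.

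**Conclusion.** The gap holds as an omission in eligibility: patients previously treated with AZR-MD-001 could enter, and the criteria would tilt any who did towards tolerators who did not respond or relapsed. The direction follows from the criteria; the number does not, and it may be zero.

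The sample size is sound on its own inputs and needs no change. The dilution figures rest on an assumed share and on zero effect in every returner, which is the pessimistic case. On those terms a 20% share of the active arm still leaves MGS power at 0.82 to 0.87. The tolerability effect cannot be sized from the documents.

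This is a cheap improvement that removes a foreseeable selection problem from a small safety and tolerability trial. It does not invalidate the design.

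**What to change.** Add one line to Section 5.2 and the synopsis excluding prior exposure to AZR-MD-001. Patients known to have received only vehicle in an earlier study need not be excluded.

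If the sponsor prefers to keep previously exposed patients, the protocol should say so and the CRF should record prior exposure. The SAP should then add a sensitivity analysis of MGS, Total OSDI and the tolerability questionnaire without them.

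The first option costs an amendment of one criterion and a small loss of easily found candidates at sites that ran AZ201801. The second costs one CRF item and one extra set of tables, and at this sample size the re-analysis would be descriptive.
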